Methodology	
Two cohorts of 8 eligible subjects each will receive 5 once-weekly 60-minute infusions of SYNT001 in planned doses of 10 mg/kg or 30 mg/kg. Based on review of safety, PD, and clinical outcomes of these 2 cohorts, a third cohort of up to 8 subjects may be treated at another dose, with a maximum dose of 45 mg/kg, but may also be lower than 10 mg/kg or between 10 and 30 mg/kg, inclusive.
 
  
 Cohort	No. of subjects	Dose	
   
 1	8	SYNT001 10 mg/kg	
 
 2	8	SYNT001 30 mg/kg	
  
 
Cohorts will be dosed sequentially beginning with Cohort 1. The first 2 subjects will be dosed at least 24 hours apart. A review of the 24-hour safety data for the first subject will be performed to ensure that there are no overt safety concerns before dosing the second subject. A review of the 7-day safety data for the first 2 subjects will be performed prior to dosing the remaining 6 subjects in the cohort. This evaluation will include a review of AE/SAE reports, vital sign assessments, physical examinations, ECGs, and clinical laboratory testing. The seriousness, severity, and relatedness of AEs/SAEs will also be considered in the safety evaluation. Safety data will be reviewed on a continuous basis throughout the study. All safety data and any available and relevant PD data through Day 42 (2 weeks after the last subject's last dose in Cohort 1) will be reviewed by a dose escalation committee before Cohort 2 is initiated. Escalation to Cohort 2 will proceed if there are no concerning safety signals and the review of available and relevant PD data supports advancing to a higher dose. The dose for Cohort 2 will be finalized after review of the safety and PD data, but will not exceed 30 mg/kg. Cohort 2 and Cohort 3, if added, will be dosed per the same schedule as Cohort 1.
 
On days where study drug is administered, vital sign and pulse oximetry measurements will be collected immediately prior to the infusion; 15, 30, and 45 minutes after the start of the infusion; at completion of the infusion; and 30 minutes, 1 hour and 2 hours following completion of the infusion.
 
On Days 0 and 28, PK blood samples will be collected prior to infusion start and then over the subsequent 48 hours. Subjects will remain at the clinic through the 6-hour PK sample collection and will return to the clinic for the 24- and 48-hour collections. Additional samples will be collected on Days 5 and 33.
	Cohort	No. of subjects	Dose	1	8	SYNT001 10 mg/kg	2	8	SYNT001 30 mg/kg

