Dose-escalation rules	
Dose-limiting toxicity (DLT) will be defined generally as clinically significant, severe (Grade 3) AEs occurring in <math>\geq 2</math> subjects that are determined to be clinically significant and considered related to study drug.
 
If 2 or more subjects at any time in any cohort (8 total subjects per cohort) have Grade 3 AEs that are determined to be clinically significant and considered to be related to study drug, dosing will be halted within that cohort and no further dose-escalation will occur. If the dose-escalation stopping rule is met in Cohort 1 (10 mg/kg) all safety data and all available pharmacodynamics data will be reviewed and a cohort may be added at a dose at least 50% lower than the 10 mg/kg dose. If the stopping rule is not met after Cohort 1 (10 mg/kg), dose-escalation may proceed up to a maximum of 30 mg/kg. If the dose-escalation stopping rule is met in Cohort 2, all safety data and all available pharmacodynamics data will be reviewed and a cohort may be added at a dose at least 30% lower than the Cohort 2 dose. If the stopping rule is not met after Cohort 2, dose-escalation may proceed up to a maximum of 45 mg/kg; however, this cohort may also receive a dose equal to or less than 30 mg/kg based on evaluation of all safety and pharmacodynamic data.

Study stopping rule	
If any subject experiences a life-threatening AE (Grade 4) that is considered to be related to study drug, any further dosing in all enrolled subjects will be suspended until the DEC has evaluated the event and determined the next appropriate course of action. At any time during the study, the study may be discontinued if the DEC determines that further drug exposure would pose an undue risk to subjects.

Individual stopping rule	
Dosing for any individual subject will be discontinued (i.e., further treatment with the study drug will not be given) if the subject experiences any study drug-related SAE or any study drug-related non-SAE adverse event that, in the judgement of the Investigator and Medical Monitor, suggest that it could be unsafe to administer further study drug to that subject. Additionally, a subject may be discontinued from further treatment with study drug, at the discretion of the Investigator with consultation with the Medical Monitor, if they require a

	significant increase in dose(s) of anti-pemphigus medication(s) for the management of pemphigus.

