Safety evaluations will be conducted by a dose escalation committee (DEC). The DEC will consist of the Medical Monitor, an Independent Clinical Expert and a Syntimmune Medical Officer. To assist in the safety assessments, the DEC may request that Investigators, other experts, or members within their organizations review the data and participate in the discussions. Dosing and dose escalation will proceed if the DEC has determined that it would be safe and appropriate to do so. In addition, over the course of the study, the DEC will review any drug-related SAEs to determine if modifications to the study or other measures are necessary to ensure the safety of the subjects.

On days where study drug is administered, vital sign and pulse oximetry measurements will be collected immediately prior to the infusion; 15, 30, and 45 minutes after the start of the infusion; at completion of the infusion; and 30 minutes, 1 hour and 2 hours following completion of the infusion.

On Days 0 and 28, PK blood samples will be collected prior to infusion start and then over the subsequent 48 hours. Subjects will remain at the clinic through the 6-hour PK sample collection and will return to the clinic for the 24- and 48-hour collections. Additional samples will be collected on Days 5 and 33.

On Day 0 photographs will be taken of active lesions. Follow-up photographs will be taken of the same areas on Days 33 and 56. If a subject begins a steroid taper, additional photographs will be taken at the clinic visit during which the decision to begin the taper is made.

Subsequent visits will occur on Days 1, 2, 5, 7, 12, 14, 19, 21, 28, 29, 30, 33, and 42 for safety assessments, study drug dosing, sample collections, and other study procedures.

Subjects also will return to the clinic on Day 56 (28 days after receiving their last dose of study drug) for an End-of-Study/Follow-Up visit.

See [Table 1](#) for a schedule of all study events. To assess safety and tolerability, subjects will undergo physical examinations (PEs; including weight), vital sign measurements, clinical (safety) laboratory tests, AE assessments, concomitant medication assessments, and electrocardiograms (ECG).

**Note:** No vaccinations may be given from within 2 weeks of screening until 2 months following the last dose of study drug.

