## **8.4 Stopping Rule**

### **8.4.1 Dose-Escalation Stopping Rule**

Dose-limiting toxicity (DLT) will be defined generally as clinically significant, severe (Grade 3) AEs occurring in  $\geq 2$  subjects that are determined to be clinically significant and considered related to study drug.

If 2 or more subjects at any time in any cohort (8 total subjects per cohort) have Grade 3 AEs that are determined to be clinically significant and considered to be related to study drug, dosing will be halted within that cohort and no further dose-escalation will occur. If the dose-escalation

stopping rule is met in Cohort 1 (10 mg/kg) all safety data and all available pharmacodynamics will be reviewed and a cohort may be added at a dose at least 50% lower than the 10 mg/kg dose. If the stopping rule is not met after Cohort 1, dose-escalation may proceed up to a maximum of 30 mg/kg. If the dose-escalation stopping rule is met in Cohort 2, all safety data and all available pharmacodynamics will be reviewed and a cohort may be added at a dose a minimum of 30% lower than the Cohort 2 dose. If the stopping rule is not met after Cohort 2, dose-escalation may proceed up to a maximum of 45 mg/kg; however, this cohort may also receive a dose equal to or less than 30 mg/kg based on evaluation of all safety and pharmacodynamic data.

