#### **8.4.2 Study Stopping Rule**

If any subject experiences a life-threatening AE (Grade 4) that is considered to be related to study drug, further dosing in all enrolled subjects will be suspended until the DEC has evaluated the event and determined the appropriate course of action. At any time during the study, the study may be discontinued if the DEC determines that further drug exposure would pose an undue risk to subjects.

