#### 11.3.1 Serious Adverse Events

*(Notify Medpace Safety within 24 hours; document on eCRF)*

The SAE definition and reporting requirements are in accordance with Title 21 Part Code of Federal Regulations (CFR) 312.32 and the Guidance for Industry and Investigators Safety Reporting Requirements for Investigational New Drug (INDs) and Bioavailability /Bioequivalence Studies.

SAE: An AE is considered "serious" if, in the view of either the Investigator or sponsor, it results in any of the following outcomes:

- **Death:** This includes any death that occurs while the subject is "on study" as well as any death that occurs within 28 days after study drug administration.

**Note:** Death is an outcome of an AE, and not an AE. The event(s) that caused death (e.g., illness, accident) is the SAE. Death due to any other cause(s) must also be reported as an outcome of the reportable SAE.

- **Life-threatening adverse drug event:** An AE or suspected adverse reaction is considered "life threatening" if, in the view of either the Investigator or sponsor, its occurrence places the patient or subject at immediate risk of death. It does not include an AE or suspected adverse reaction that, had it occurred in a more severe form, might have caused death.

- **Inpatient hospitalization or prolongation of existing hospitalization:**

In the absence of an AE, the Investigator should not report hospitalization or prolongation of hospitalization. This is the case in the following situations:

- Hospitalization or prolongation of hospitalization is needed for a procedure required by the protocol
- Hospitalization or prolongation of hospitalization is part of routine procedure followed by study center

- Hospitalization for survey visits or annual physicals
- Hospitalization for observation with release within 24 hours

In addition, a hospitalization planned before the start of the study for a pre-existing condition, which has not worsened, does not count as an SAE.

- **Persistent or significant incapacity or substantial disruption of the ability to conduct normal life functions**
- **Congenital anomaly/birth defect**
- **Important medical event:** An event that may not result in death, be life threatening, or require hospitalization may be considered an SAE when, based upon appropriate medical judgment, it may jeopardize the subject and may require medical or surgical intervention to prevent one of the outcomes listed in this definition.

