## Grades

Grade refers to the severity of the AE. The CTCAE displays Grades 1 through 5 with unique clinical descriptions of severity for each AE based on this general guideline:

- Grade 1 Mild; asymptomatic or mild symptoms; clinical or diagnostic observations only; intervention not indicated.
- Grade 2 Moderate; minimal, local or noninvasive intervention indicated; limiting age-appropriate instrumental ADL\*.
- Grade 3 Severe or medically significant but not immediately life-threatening; hospitalization or prolongation of hospitalization indicated; disabling; limiting self care ADL\*\*.
- Grade 4 Life-threatening consequences; urgent intervention indicated.
- Grade 5 Death related to AE.

A Semi-colon indicates 'or' within the description of the grade.

A single dash (-) indicates a grade is not available.

Not all Grades are appropriate for all AEs. Therefore, some AEs are listed with fewer than five options for Grade selection.

## Grade 5

Grade 5 (Death) is not appropriate for some AEs and therefore is not an option.

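### The two-subject escalation rule in Section 8.4.1 counts only related Grade 3 events, so related Grade 4 events do not trigger the automatic bar on escalation or the cap on an added lower-dose cohort

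*Protocol*

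**What the plan says.** Section 8.4.1 defines dose-limiting toxicity by reference to severe (Grade 3) events and then gives the operative rule: "If 2 or more subjects at any time in any cohort (8 total subjects per cohort) have Grade 3 AEs", where these are clinically significant and related to study drug, dosing in that cohort is halted and there is no further escalation. If this happens in Cohort 1, a cohort may be added at a dose at least 50% below 10 mg/kg. If it happens in Cohort 2, a cohort may be added at least 30% below the Cohort 2 dose. If the rule is not met after Cohort 1, escalation is permitted up to 30 mg/kg. For the next step: "If the stopping rule is not met after Cohort 2, dose-escalation may proceed up to a maximum of 45 mg/kg".

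Section 8.4.2 covers the next grade: "If any subject experiences a life-threatening AE (Grade 4) that is considered to be related to study drug", then, in the words of the synopsis row on the study stopping rule, "any further dosing in all enrolled subjects will be suspended until the DEC has evaluated the event" and chosen the next step. It does not name Grade 5 or death. Appendix A, the adopted CTCAE scale, lists "Grade 5 Death related to AE" as a separate grade.

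Other safeguards rest on judgement. Section 4.3 states: "Dosing and dose escalation will proceed if the DEC has determined that it would be safe and appropriate to do so". The synopsis (Methodology) adds: "Escalation to Cohort 2 will proceed if there are no concerning safety signals" and the PD data support a higher dose. Section 11.5 has the DEC review all safety data through Day 42 after each cohort, and it may recommend stopping the study or lowering the dose. Section 14.5 has the DEC confirm safety before escalation and set each successive dose level.

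**The concern.** An escalation rule that counts severe events should also count worse ones. Section 8.4.1 is the only fixed numerical rule on escalation, and Section 12.8 says that no statistical analyses are planned to support those decisions. A count limited to Grade 3 leaves out the events that argue most strongly against a higher dose.

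The gap touches a foreseeable risk of this drug. Section 9.6.2 works through an 80% fall in IgG to 230 or 140 mg/dL and accepts that these levels lie in the range seen in primary humoral immunodeficiency, so serious infection is a plausible toxicity. In Appendix A, sepsis has no Grade 3 entry; it starts at Grade 4. Two subjects whose only severe related event is sepsis therefore cannot count towards the two-subject rule, whereas two subjects with related, clinically significant Grade 3 infections would.

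At stake is whether, after two such events in a cohort of 8, the bar on escalation and the minimum step-down are fixed in advance or left to the DEC.

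**Working it through.** The protocol gives no sample-size calculation (Section 12.2) and no operating characteristics for this rule, so there is no stated figure to reproduce.

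**Step 1. Apply the rules as worded.** Subjects are counted by their worst related event, taken to be clinically significant.

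| Subjects in one cohort | 8.4.1 as written | 8.4.1 with *Grade 3 or higher* | 8.4.2 as written |
|---|---|---|---|
| two Grade 3 | met | met | not triggered |
| one Grade 3, one Grade 4 | not met | met | dosing suspended |
| two Grade 4 | not met | met | dosing suspended |
| one Grade 4 | not met | not met | dosing suspended |
| one Grade 5 | not met | not met | depends on reading |
| one Grade 3, one Grade 5 | not met | met | depends on reading |
| two Grade 5 | not met | met | depends on reading |

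A subject with a Grade 4 event who also had a separate related, clinically significant Grade 3 event would still count under the present wording. The table ignores that.

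**Step 2. The dose ceilings that drop out.** After Cohort 1: 10 × (1 − 0.50) = 5 mg/kg. After Cohort 2: 30 × (1 − 0.30) = 21 mg/kg if Cohort 2 ran at 30 mg/kg, and lower if its dose was lower.

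**Step 3. Illustrative size.** The protocol gives no event rates in pemphigus. Section 2.2 reports no dose-limiting toxicities or serious adverse events in Phase 1a, which used single doses in healthy men. The rates below are therefore assumptions. Let p3 and p4 be the per-subject chances that the worst related event is Grade 3 or Grade 4, with n = 8 and independent subjects. Grade 5 is not modelled.

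- Bar as written: 1 − (1 − p3)^8 − 8·p3·(1 − p3)^7.
- Bar with *Grade 3 or higher*: the same formula with p3 + p4 in place of p3.
- At least one of 8.4.1 and 8.4.2 fires: 1 − [(1 − p3 − p4)^8 + 8·p3·(1 − p3 − p4)^7].

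For p3 = 5% and p4 = 2%:

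- As written: 1 − 0.95^8 − 8(0.05)(0.95^7) = 1 − 0.6634 − 0.2793 = 0.057.
- Corrected: 1 − 0.93^8 − 8(0.07)(0.93^7) = 1 − 0.5596 − 0.3370 = 0.103.
- Either rule: 1 − [0.5596 + 8(0.05)(0.6017)] = 0.200.

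| p3 / p4 (assumed) | Bar as written | Bar corrected | Difference | Either rule fires |
|---|---|---|---|---|
| 2% / 1% | 1.0% | 2.2% | 1.2 points | 8.7% |
| 5% / 2% | 5.7% | 10.3% | 4.6 points | 20.0% |
| 10% / 5% | 18.7% | 34.3% | 15.6 points | 47.1% |

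The last column is the same before and after the correction. Every case added to the bar contains at least one related Grade 4 event, and Section 8.4.2 has already suspended dosing for it. The difference column therefore counts cases that move from a DEC decision to an automatic bar, not cases that move from unprotected to protected.

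**The case against.** The strongest reply is that the two rules are tiered, and that the tier for worse events is the stricter one. Two Grade 3 subjects halt one cohort; a single related Grade 4 event suspends dosing in every enrolled subject. An unmet Section 8.4.1 only permits escalation. It does not direct it, and Sections 4.3, 11.5 and 14.5 require the DEC to judge escalation safe and let it stop or step down after any cohort. The dose-limiting toxicity definition is also qualified as general, which leaves room for judgement. All of this stands as to whether dosing is guarded. It does not supply the missing bar: Section 8.4.2 is a pause that ends in discretion, and the operative two-subject sentence does not carry the general qualifier.

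Several stronger readings are tempting, and the documents do not support them.

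- A reader might infer that life-threatening events get weaker protection overall, or that escalation would simply continue after two of them. The study-wide suspension and the required DEC determination rule that out.
- A reader might infer that two Grade 3 subjects force a lower dose. The lower-dose cohort is optional; only its ceiling is fixed.
- A reader might infer that the step to 45 mg/kg has no safety condition because the quoted synopsis condition concerns Cohort 2. Section 4.3 makes a third cohort depend on review of safety, PD and clinical outcomes from both earlier cohorts, and Section 11.5 applies after each cohort.
- A reader might infer that a related death triggers nothing. Section 11.3.1 treats death as the outcome of an event and calls an event life-threatening when "its occurrence places the patient or subject at immediate risk of death". A related event that proves fatal is naturally covered by Section 8.4.2 despite its Grade 4 label, and drug-related serious events go to the DEC in any case.

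**Conclusion.** The point holds as a defect in a stated rule. Read literally, the two-subject rule omits Grade 4 and above, and no other section extends it. The protocol uses the inclusive form elsewhere: the title of Figure 2 on infusion reactions covers Grade 3 or higher. The consequence is limited. After two related Grade 4 subjects, or one Grade 3 and one Grade 4, the bar on escalation and the cap on an optional added cohort become matters for the DEC instead of following automatically.

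Under the assumed rates, between 1.2 and 15.6 percentage points of cohorts fall in that gap. These figures rest on assumed rates, independent subjects and counting by worst grade; the finding itself rests only on the wording. The absence of Grade 5 from Section 8.4.2 is a matter of clarity, not a second defect.

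**What to change.** In Section 8.4.1, write *Grade 3 or higher* in both the dose-limiting toxicity definition and the two-subject rule, and do the same in the synopsis row on dose-escalation rules. As a clarification only, write *life-threatening or fatal AE (Grade 4 or 5)* in Section 8.4.2 and in the synopsis row on the study stopping rule.

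The cost is a few words, with no new data and no change in sample size. The price is a somewhat higher chance of ending escalation when related Grade 4 or higher events occur, as shown above for Grade 4. When dosing is first suspended for a Grade 4 event does not change.

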
Safety assessments
	
Safety assessments include AEs, serious adverse events (SAEs), PEs, vital sign measurements, clinical safety laboratory evaluations, ECGs, and reasons for treatment discontinuations due to toxicity. Safety assessments will be performed at specified time points and prior to discharge from the clinic. Vital sign measurements, including blood pressure, pulse rate, respiratory rate, and temperature will be monitored throughout the study. Pulse oximetry will be monitored during the study drug infusion and for 2 hours following the end of the infusion.
 
The National Cancer Institute Common Terminology Criteria for Adverse Events (NCI CTCAE; Version 4.03) will be used for grading clinical and laboratory AEs.

	
The AE reporting period for a subject enrolled in the study begins when the subject provides informed consent and is continued for 28 days after the last dose of study drug. All AEs that occur in the enrolled subjects during the AE reporting period must be recorded, regardless of the relationship of the AE to study drug. Any known untoward event that occurs beyond the AE reporting period that the Investigator assesses as related to study drug should also be recorded.

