### 6.10 Adverse Event Assessments

Information regarding the occurrence of AEs will be collected from the time the subject signs the informed consent form throughout their participation in the study, including a period of 28 days after study drug dosing. Findings at screening and Day 0 (pre-dose) will be recorded as medical history. Any known untoward event that occurs beyond the AE reporting period that the Investigator assesses as related to study drug also should be reported as an AE.

Clinical AEs will be graded using the NCI CTCAE, Version 4.03 ([Appendix A](#)).

**Note:** AEs resulting in a subject's permanent discontinuation from the study, regardless of seriousness or relationship to study drug, MUST be promptly reported to the sponsor. Additionally, subjects must be followed until return to normal and/or resolution of the AE.

See [Section 11](#) for more information.

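### A toxicity trigger in Cohort 1 that comes after its Day 42 review stops no infusion, and no sentence holds subjects already on the higher dose while the required review is done

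*Protocol*

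**What the plan says.** **The trigger.** Section 8.4.1, repeated in the synopsis under the dose-escalation rules, opens with "If 2 or more subjects at any time in any cohort (8 total subjects per cohort) have Grade 3 AEs". The events must be clinically significant and related to study drug.

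**The consequence.** Once the trigger is met, "dosing will be halted within that cohort and no further dose-escalation will occur". If the cohort is Cohort 1 or Cohort 2, "all safety data and all available pharmacodynamics will be reviewed" and a lower-dose cohort may be added. If the rule is not met after Cohort 1, escalation may go up to 30 mg/kg.

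**When Cohort 2 may open.** The synopsis (Methodology) says that safety data and available PD data through Day 42 "will be reviewed by a dose escalation committee before Cohort 2 is initiated". Sections 4.3 and 11.5 agree on Day 42.

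**How long events are collected.** The synopsis says the reporting period "is continued for 28 days after the last dose of study drug", which is nominally Day 56. Section 6.10 goes further: "Any known untoward event that occurs beyond the AE reporting period that the Investigator assesses as related to study drug" is also to be reported as an AE.

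**The contrast with Grade 4.** Under Section 8.4.2, after one related Grade 4 event, "further dosing in all enrolled subjects will be suspended until the DEC has evaluated the event". The same section adds that "the study may be discontinued if the DEC determines that further drug exposure would pose an undue risk to subjects".

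**The concern.** The trigger is open-ended in time, but the automatic halt reaches only the cohort that set it off. These two features fit together while that cohort is still being dosed. They part once its dosing is over and a higher-dose cohort is running.

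The rule exists to stop exposure when a dose proves too toxic. If 10 mg/kg first meets the rule while subjects are on 30 mg/kg, the automatic halt stops no infusion. The people at greatest risk continue unless someone chooses to intervene. The protocol requires a review at that point but does not say that dosing waits for it.

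Late events are plausible. Section 9.6.2 expects IgG reductions of up to 70% to 80% after multiple doses, with recovery within 4 weeks (the multiple-dose figure comes from non-human primates), and says subjects will be monitored for infection. Four weeks after the Day 28 dose is Day 56, so low IgG may extend past the Day 42 cut.

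**Working it through.** The protocol gives no operating characteristic for this rule, so there is no figure to reproduce. The check is mainly one of text and calendar.

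**1. Timing.** Inputs: last dose Day 28, review cut Day 42, scheduled end of AE collection Day 56 (synopsis, 4.3, Table 1).
- Dosing left in Cohort 1 after Day 42: none.
- Nominal overlap for the last Cohort 1 subject: 56 − 42 = 14 days. With a Cohort 2 start lag of L days after that Day 42, it is max(0, 14 − L).
- Table 1 allows ±3 days around Day 42. A Day 39 visit gives 56 − 39 = 17 days, so 14 is not a strict upper limit.
- Related events reported after Day 56 fall outside this window and can still arise.

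**2. Dose ratio.** 30/10 = 3 for Cohort 2 against Cohort 1. If Cohort 3 goes to its maximum, 45/30 = 1.5 against Cohort 2. If Cohort 3 is at or below the Cohort 2 dose, the issue does not arise for that pair.

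**3. What each safeguard does if Cohort 1 first triggers after Cohort 2 has opened.**
- 8.4.1: halts Cohort 1 (nothing left to halt), bars further escalation and requires a review. No hold on Cohort 2 is stated.
- 8.4.2: automatic suspension for all subjects, but only for a related Grade 4 event; otherwise DEC discretion.
- 8.4.3: stops the affected subject only.
- 4.3: dosing proceeds if the DEC has judged it safe and appropriate; no interim hold is stated.
- 8.2: the sponsor may stop the study; discretionary.
- 11.3.9.2: 24-hour report to the sponsor or designee. Non-serious severe events are covered only if unexpected, and the report does not itself pause dosing.
- 4.3 and 14.5: the events named for DEC review during the study are drug-related SAEs. A qualifying Grade 3 event need not be serious.

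**4. Who could be on the higher dose.** Section 9.2 sets the fastest stagger: subject 1 at L, subject 2 at L + 1, the other six at L + 8 (after 7-day data on the first two), each then dosed weekly. Full course: 8 × 5 = 40 infusions. Position when the last Cohort 1 subject reaches Day 56 (day 14 counted from that subject's Day 42):

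| Lag L (days) | Started | Infusions given | Left for those started |
|---|---|---|---|
| 0 | 8 | 3 + 2 + 6 = 11 | 40 − 11 = 29 |
| 1 to 6 | 8 | 2 + 2 + 6 = 10 | 40 − 10 = 30 |
| 7 | 2 | 2 + 1 = 3 | 10 − 3 = 7 |
| 8 to 13 | 2 | 1 + 1 = 2 | 10 − 2 = 8 |

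Lag 0 needs a same-day start and is unlikely.

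**5. How often (illustration only).** Assumed, not in the protocol: each of 8 Cohort 1 subjects has chance p = 10% to 20% of a qualifying event; a share f = 10% to 25% of that falls after Day 42, spread evenly; k subjects have just reached Day 42 at lag zero and the rest have passed Day 56. For those k, the chance of an event before Cohort 2 opens is p(1 − g), with g = f(14 − L)/14. With B the number of subjects with events before opening and T the total, P(first met after opening) = P(B ≤ 1) − P(T ≤ 1).

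Worked case, p = 0.10, f = 0.10, L = 0, k = 1:
- P(T ≤ 1) = 0.9⁸ + 8 × 0.1 × 0.9⁷ = 0.8131.
- P(B ≤ 1) = 0.9⁷ × 0.91 + (7 × 0.1 × 0.9⁶ × 0.91 + 0.9⁷ × 0.09) = 0.4353 + 0.3816 = 0.8168.
- Difference: 0.37%.

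Ranges from (p, f) = (0.10, 0.10) to (0.20, 0.25):
- L = 0: 0.37% to 1.84% (k = 1); 1.48% to 7.52% (k = 4).
- L = 7: 0.19% to 0.92% (k = 1); 0.74% to 3.72% (k = 4).

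**The case against.** **The rule may already close new entry.** It bars further escalation, and permission to go to 30 mg/kg depends on Cohort 1 not having met the rule. Since the trigger runs at any time, a late trigger can be read as withdrawing that permission, so that no new subject starts in Cohort 2. This is a fair reading. A reader might instead infer that new Cohort 2 starts would simply continue; the text does not establish that. But it does not state the bar clearly either, and it does not reach subjects in mid-course. Those subjects are the core of the point.

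**Dosing is not unsupervised.** Section 4.3 makes dosing itself subject to DEC judgement, safety data are reviewed continuously, and a trigger requires a full review. Cohort 2 has its own two-subject halt, the individual stopping rule and a 7-day review before the remaining six are dosed. The table's counts of eight started assume that review passes despite any Cohort 1 events already known. Many Grade 3 infections would probably be serious and so reach the DEC singly. All this stands, so it would be wrong to infer that Cohort 2 is unprotected. What is missing is narrower: an explicit hold while the review is done, and a stated route to the DEC for related Grade 3 events that are not serious.

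**The tiering is defensible and the scenario rare.** A cohort-level halt for Grade 3 beside a study-wide suspension for Grade 4 is a reasonable design. The upper probabilities need even risk over 56 days (14/56 = 25%), whereas infusion reactions come within about a day (9.6.1) and the single-dose IgG nadir falls near Day 5 (9.6.2). They also need zero lag and several Cohort 1 subjects in the window. This stands, and the probabilities should carry little weight.

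**Conclusion.** The point holds in a limited form. If Cohort 1 first meets the Grade 3 rule after its Day 42 review, the automatic halt has no effect, and nothing written holds subjects already being treated in an open Cohort 2, at up to three times the dose, while the required review takes place. The same applies between Cohorts 2 and 3 only if Cohort 3 opens at a higher dose.

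The exposure is limited by the calendar: nominally 14 days, somewhat more with visit windows, none if the start lag is of similar length, apart from related events reported later. The scenario is uncommon. The probabilities rest on event rates and timing that the protocol does not give, and are illustrative only. No sample size, error rate or power figure is affected. The conclusion rests on the wording of 8.4.1 rather than on those figures. This is a cheap improvement to a safety rule.

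**What to change.** Keep the halt in the triggering cohort as it is. Add to Section 8.4.1 and to the synopsis dose-escalation rules:

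> If the rule is met in a cohort after a higher-dose cohort has opened, no new subject starts and further dosing is suspended in that higher-dose cohort until the DEC has reviewed the events and decided how to proceed.

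State in Sections 11.5 and 14.5 that related, clinically significant AEs of Grade 3 or higher, serious or not, that arise in an earlier cohort after its Day 42 review go to the DEC as they occur.

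This follows the mechanism that 8.4.2 already uses for Grade 4 events. It needs no extra subjects, visits or samples. The cost is a possible short pause: Table 1 allows only ±4 to ±6 hours around the post-baseline dosing days, so a weekly dose could be delayed or missed.
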